**Impact of physical activity on cognitive outcomes in youth with pediatric-onset
multiple sclerosis**

NCT03933020

Version Date: 04/24/2019

Protocol Title:	Impact of physical activity on cognitive outcomes in youth with pediatric-onset multiple sclerosis
Principal Investigator:	[name]; [name]
Co-Investigators:	[name], PhD; [name] ; [name] ; [name] ; [name] ; [name], PhD ; [name] , MD
Study Coordinator:	[name]
Population:	24 subjects aged \leq 25 years with a confirmed diagnosis of Pediatric-Onset Multiple Sclerosis (POMS)
Number of Sites:	UT Houston
Study Duration:	1 year
Subject Duration:	6 months of intervention, 6 months follow-up

General Information

Pediatric Onset Multiple sclerosis (POMS) is associated with a higher disease burden compared to adults with frequent relapses early in disease¹, a higher load of T2 lesions on magnetic resonance imaging (MRI)² and a more prevalent risk of motor and cognitive disability by early adulthood. Although disease modifying therapies (DMT) remain the mainstay to long term management of POMS, the identification and control of environmental contributing factors has a significant impact on disease course. A sedentary lifestyle and obesity in childhood can lead to an increased risk for POMS³ and lower physical activity is associated with a higher disease burden in adolescents with MS⁴. Furthermore, youth with MS self-report lower levels of physical activity compared to healthy controls⁵. They also present higher rates of fatigue and depression symptoms⁶, cognitive impairment⁷, as well as overall reduced health-related quality of life compared to their healthy peers⁸. Exercise has been proven the single most effective non-pharmacological approach to manage disabilities and improve quality of life in adults with MS⁹⁻¹¹. Such beneficial effects are equally probable in children with MS but are only just emerging and their maintenance across a lifespan remains difficult in this age group.

Background Information

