We aim to conduct a single-center randomized controlled trial to measure the impact of physical activity through virtual reality video games on the motor and cognitive performance of youth with MS. Through such a home-exercise program coupled with patient online behavior counseling, we hypothesize that we can significantly impact subjective and objective measures of disease disability in this MS age population.

Objectives

Primary objective: to assess the impact of a virtual reality video (VR) game exercise program on **objective cognitive assessments in youth with MS** (measures outlined below). The **null hypothesis** for this study is that there is no difference in the **Brief Cognitive Assessment for MS** in cognitive disability of youth with MS between those enrolled in a 6-month VR active video game program and those with routine follow-up care. The alternative hypothesis is that there is a difference in measures of cognitive disability between the two groups (two-sided hypothesis).

Secondary objectives:

- To determine the impact of VR physical activity on subjective measures of cognitive, physical and psychosocial disability in youth with MS
- To determine the impact of VR physical activity on the 6-Minute Walk Test (6MWT).

- To determine the number of clinical relapses and new T2 MRI lesions (brain)
- To determine the **safety** of implementing a VR active video game program at home
- To evaluate the effect of VR exercise programs on overall behavior towards physical activity and health promotion in youth through self-report questionnaires

Study Design

- **Single-center, single blinded, randomized controlled trial** comparing a 6-month VR active video game intervention with standard management of physical activity in youth with MS.
- Each participant will be randomly allocated to either the intervention group or the control group for a **period of 6-months** with pre- and post- assessments performed at onset, 3 months, 6 months and 12 months follow-up.
- The study will be conducted over one year with 6 months of intervention. Each group will include 12 subjects (**total subjects = 24**).
- The Microsoft VR active game program will consist of 3 weekly sessions of 45 minutes each combining 3 different types of exercise (cardiovascular and strength with 'Box VR', flexibility with 'Beat Saber', coordination with 'The Climb').

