- To assess the impact of the VR exercise program, a series of subjective and objective assessments will be performed prior to onset, at 3 months, upon completion at 6 months and at 12 months follow-up. These assessments are detailed in the section 'Study procedures' below.
- **Assessment of safety** will be conducted throughout the intervention and will consist of self-reported incidents that occur during the exercise sessions, including falls or physical injuries. These events will be recorded at 1 month, 3 months and 6 months from onset by the investigators.
- **Assessment of adherence** to the program will be documented throughout the study via anonymized exercise logs provided by Microsoft that will monitor participation and overall performance for each game. Microsoft will also provide customer service for any technical difficulties with the VR headsets provided.
- **Personal sessions** with each participant in the intervention group will be conducted via phone calls to educate them on the importance of exercise and assess for any difficulties to adhere to sessions. They will take place at 1 month, 3 months and 6 months. Furthermore, a survey questionnaire will be given to all participants enrolled in the intervention group at the 6-month follow-up time to determine the degree of incorporation of physical activity into their daily life following completion of the study.

Study Population

- Inclusion criteria: (1) **age between 15-25 years**, (2) **confirmed diagnoses of Pediatric-Onset MS (<18 years)** according to the 2017 revised McDonald criteria (relapsing-remitting), (3) **Expanded Disability Status Scale (EDSS) ≤ 5.0**, (4) **relapse free for the past 30 days**, (5) **no contraindications to physical activity**, including pregnancy (6) no history of visual provoked seizures and (7) participant and parent (if between 15 and 18 years of age) **written informed consent**.
- The participants will be recruited through the neurology clinic in Houston using phone, email or postal communications. People who are interested in taking part will be contacted by the research team via phone or email and explained the study in detail. If the selection criteria are met, informed consent forms and participant information leaflets will be sent via post or email, or obtained during a routine clinic visit.

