- The subjective assessments will be mailed to the participants or given when seen in clinic. Study staff will perform the 6MWT at the time of a routine clinic visit and will require no additional costs.
- The three cognitive assessments per subject will be carried out by a qualified neuropsychologist or neurologist and will be performed at the time of a routine clinic visit.

Data and Safety Monitoring

- During the course of study participation, subjects might experience an adverse event related to the physical activity or to their underlying MS. These events might include falls, musculoskeletal injuries, neurological symptoms suggestive of a clinical relapse, or any other physical or psychological cause of distress. These events will be documented by participant self-reports and contacting study personnel. They will be graded from 1 to 3 according to their degree of severity with 1 = mild, no interference with daily activities, 2 = moderate, some interference with daily activities and 3 = severe, significant interference with daily activities and requiring medical intervention.
- The research team will perform a **periodic review of adverse events** recorded once every 2 months as well as an assessment of adherence to the exercise programs and any other concerns raised by the research team or the participants.
- In the event of a clinical relapse or worsening of a participant's neurological symptoms, the research team will promptly inform the MS specialist in charge of that participant's care. Subject's participation in the intervention group will cease.

Statistics

- Statistical analysis will be performed using the software program **Stata version 15**.
- Descriptive numerical or graphical summaries will be used for demographic and clinical characteristics of the sample population at baseline. Independent samples t-tests and chi-square tests will be done to assess differences between intervention and control groups on pre-trial and post-trial assessments. Only participants who completed the 6-month exercise program will be included in the analysis of the intervention group but missing data will be noted. Paired sample t-tests and chi-square tests will be conducted to determine differences in pre-trial and post-trial assessments within each group. If data reveals a skewed distribution, Kruskall Wallis tests will be used for continuous variables. All tests will be conducted using an alpha = 0.05 level of statistical significance.

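### The relapse count has no window and no scheduled collection, and the only scheduled event recording reaches the intervention arm alone

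*Combined protocol and SAP*

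**What the plan says.** The secondary objectives include "To determine the number of clinical relapses and new T2 MRI lesions (brain"), and, separately, the safety of the home program. No section gives the relapse count a time window, a definition, an assessor or a collection visit.

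Two sections describe how events are gathered.

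- **Study Design, assessment of safety.** It runs through the intervention and "will consist of self-reported incidents that occur during the exercise sessions, including falls or physical injuries". The next sentence gives the timing: "These events will be recorded at 1 month, 3 months and 6 months from onset by the investigators". The personal phone sessions, held at the same three months, are for the intervention group only.
- **Data and Safety Monitoring.** The scope is wider: "During the course of study participation, subjects might experience an adverse event related to the physical activity or to their underlying MS". The examples include "neurological symptoms suggestive of a clinical relapse". Capture is passive: "These events will be documented by participant self-reports and contacting study personnel". The team reviews recorded events every 2 months, with no end date given.

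The synopsis sets subject duration at "6 months of intervention, 6 months follow-up". Study Procedures gives both arms questionnaires at weeks 1 and 12 and at 6 and 12 months, and cognitive and walking assessments at enrollment, 6 and 12 months. Relapse and adverse-event history appear in none of these lists.

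**The concern.** Relapses and harms are to be compared between two arms of 12. For that comparison to mean anything, both arms must be asked the same questions at the same times over the same period. As written, the intervention arm has scheduled calls and incident recording. The control arm has no scheduled contact at which events are said to be raised. A difference in counts could then reflect who was asked and not who relapsed.

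The missing window adds a second problem. Either a 6-month or a 12-month count would satisfy the objective, so the choice could be made after the data are seen.

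**Working it through.** The plan states no relapse rate, expected count or event target, so there is no figure of its own to reproduce.

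**Step 1. The event provisions side by side**

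| Section | Events | Period | Arm reached | Capture |
|---|---|---|---|---|
| Objectives | Relapses | Not stated | Not stated | Not stated |
| Study Design, safety | Incidents in exercise sessions | Intervention; months 1, 3, 6 | Intervention | Self-report, recorded by investigators |
| Study Design, personal sessions | Adherence difficulties, education | Months 1, 3, 6 | Intervention | Phone call |
| Data and Safety Monitoring | All adverse events, including possible relapse | Study participation (6 + 6 = 12 months) | Both | Participant reports or contacts staff |

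Scheduled contacts specific to one arm at which an event could naturally come up: 3 in the intervention arm, 0 in the control arm. Relapses have no scheduled collection in either half-year.

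**Step 2. Effect of unequal capture.** Let both arms have the same true rate, and let c_I and c_C be the proportions of events captured. The expected observed rate ratio is c_I / c_C, which equals 1 only if capture is equal. The documents give no basis for values of c_I or c_C, so no size is put on this.

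A second mechanism pulls the other way. Under Data and Safety Monitoring, a relapse ends participation in the intervention group. Statistics limits the intervention arm, but not the control arm, to program completers. Applied to the relapse count, that removes intervention participants who relapse before completing and keeps controls who relapse. The net direction cannot be read from the plan.

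**Step 3. Effect of the undefined window.** Inputs: N = 24 ("Each group will include 12 subjects"); T = 0.5 or 1 year; an assumed relapse rate r of 0.2 to 1.0 per person-year, constant and equal in the two arms; no dropout.

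- All relapses: N × r × T.
- First relapses only: N × (1 − exp(−rT)). The 12- to 6-month ratio is 1 + exp(−r/2).
- Mixed: first relapse only in the intervention arm (12), all relapses in the control arm (12).

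| r | All: 6 mo, 12 mo, ratio | Mixed: 6 mo, 12 mo, ratio | First only: 6 mo, 12 mo, ratio |
|---|---|---|---|
| 0.2 | 2.4, 4.8, 2.00 | 2.34, 4.58, 1.95 | 2.28, 4.35, 1.90 |
| 0.5 | 6.0, 12.0, 2.00 | 5.65, 10.72, 1.90 | 5.31, 9.44, 1.78 |
| 1.0 | 12.0, 24.0, 2.00 | 10.72, 19.59, 1.83 | 9.44, 15.17, 1.61 |

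**Step 4. Why a rate and not a raw count.** In the mixed case with r = 1.0, the 12-month counts are 7.59 (intervention) and 12.0 (control) although the true rates are equal. Person-years in the intervention arm are 12 × (1 − exp(−1)) / 1.0 = 7.59, so its rate is 7.59 / 7.59 = 1.0, as in the control arm. Person-time removes the artefact.

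**Step 5. Precision of the two candidate windows.** With E = 12 × r × T expected relapses per arm, the approximate 95% CI for the rate ratio extends by a factor exp(1.96 × √(2/E)) on each side.

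- r = 0.3: E = 1.8 at 6 months (factor 7.9) and 3.6 at 12 months (4.3).
- r = 1.0: E = 6 at 6 months (3.1) and 12 at 12 months (2.2).

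On the log scale the 12-month interval is 1/√2 = 0.71 times as wide, or 29% narrower, whatever the constant rate. The approximation is rough at counts this low.

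**The case against.** A reader might infer that the plan stops recording relapses at month 6 in one section and continues to month 12 in another. The documents do not support this. The events recorded at months 1, 3 and 6 are exercise-session incidents, so it is consistent for that recording to end with the program. Data and Safety Monitoring describes a wider class of events. The two sections differ in scope and do not set two end dates for relapses. It follows that the plan does not discard relapse time after month 6. Nor is there a shown under-count peculiar to months 7 to 12, because self-report is the stated route for relapses throughout.

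Further points on the plan's side:

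- The 2-monthly review has no end date, and an MS specialist sees participants for the walking test at 6 and 12 months. Staff may well learn of relapses there. But the review covers events already recorded, and the clinic assessment does not list relapse history.
- The study schedule and data acquisition form are listed as attachments but are not shown. They may contain relapse items. This stands as a limit on the finding. It would not supply the window missing from Objectives or align the two safety descriptions.
- The twofold ratio is only 12 months over 6 months. It needs a constant rate, complete follow-up and every relapse counted, so it is an upper value.
- Adverse-event questions could reveal group membership, and Quality control and assurance requires blinded assessors. This is fair, and the fix allows for it.

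**Conclusion.** The point holds as an omission with a between-arm consequence. In the visible text, a secondary outcome has no window and no scheduled collection. The only scheduled event recording and calls reach one arm. Relapses and all other adverse events rest on unprompted reports.

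The choice of a 6- or 12-month window changes the expected relapse count by about 1.6 to 2 times. That range rests on an assumed constant rate of 0.2 to 1.0 per person-year, equal arms and no dropout, and on whether repeat relapses count. The distortion from unequal contact is real in principle, but the documents do not allow its size or net direction to be estimated. The primary cognitive outcome is not affected. The change is worth making because it is cheap and because 12 per arm leaves little relapse information to lose.

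**What to change.** - **Window.** State in Objectives that relapses and adverse events are counted from randomization to month 12 in both arms. Reconcile the assessment of safety in Study Design and Data and Safety Monitoring with that statement.
- **Collection.** Add one identical, structured relapse and adverse-event question set for both arms to the self-report packet already distributed at week 12, month 6 and month 12. Have it returned to staff who are not the blinded assessors.
- **Reporting.** Report exercise-session incidents separately, for the intervention arm only. Report relapses per person-year over 12 months for all randomized participants, and also show months 0–6 and 7–12.

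The cost is a wording change in three sections and a few added questions, with no new visit. There is a small risk of unblinding, limited by keeping the answers from the assessors. If the unseen schedule or data form already holds such items, the collection step reduces to citing them and confirming that they are the same for both arms.

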- Participants will be **randomly allocated in blocks** to either the intervention or control group, and the allocation group will be **concealed from the study personnel** that are analyzing the data.

Study Procedures

- Subjects in the intervention group will receive a Samsung Windows Mixed Reality headset with motion controllers that links to their PC/laptop. They will be given 3 different VR video games (Box VR, Beat Saber and The Climb) at onset. They will be instructed to play a minimum of 3 sessions per week, one session on each game, for the first 3 months. They will have the possibility of dropping one game for the remaining 3 months but maintaining a minimum of 3 sessions per week. Each session will last 45 minutes. They may play more than 3 sessions per week but will be required to document additional time.
- **Exercise logs** will be provided to document weekly sessions for monitoring adherence. Participants in both groups will be asked to document any sport activities performed during the study period, with an estimate of duration per week and type of activity, to account for physical activity done outside of the active intervention. This will be recorded during the 6-month intervention period.
- The intervention group will also receive two **education discussion sessions** on the benefits of exercise for people with MS. The investigator MS specialists will conduct these sessions either by phone or at the time of a clinic visit and will also discuss difficulties encountered by participants with adherence.
- A neuropsychologist or MS specialist will perform an **objective cognitive assessment** at the time of enrollment, at 6 months and at 12 months follow-up, consisting of the **Brief International Cognitive Assessment for MS (BICAMS)**, which includes three subtests:
 - **Symbol Digit Modalities Test (SDMT)**, a measure of sustained attention, working memory and information processing speed
 - **California Verbal Learning test – II (CVLT-II)**, a measure of verbal memory (immediate recall) including the first 5 recall trials
 - **Brief Visuospatial Memory Test (BVMT) - Revised**, a measure of visuo-spatial learning and delayed recall, using the first 3 recall trials

The battery takes 15 min to complete, requires no specialist equipment and no specialist expertise in cognitive assessment.

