- Qualitative analysis will be performed through a survey questionnaire collected at the time of the 6-month follow-up, to determine participants' experience and longer term perspectives with regards to the integration of physical activity in the management of their disease.
- The selection of subjects to be included in the analyses will comprise all of those randomized to the control group and all of those randomized to the intervention group who completed the 12-week

exercise program. Dropouts at all stages (enrollment, randomization, intervention, 6-month follow-up) will be recorded.

Ethics

- IRB approval will be sought from CPHS prior to initiation of this study.
- Prior to enrollment in the study, all subjects and parents will be explained all parts of the research in a detailed manner by one of the study investigators. This will be conducted in a quiet environment either at the UT Clinic or by phone. Participants will be given the opportunity to ask questions during the consent process and at any time for the duration of the study. There will be no time limit to obtaining patient consent. Subjects will also be allowed to withdraw their consent at any time by contacting one of the study's investigators.

Data handling and record keeping

- Upon obtaining informed consent from each participant and all selection criteria met, study personnel will access demographic characteristics and all clinical data relevant to MS. This will include past and current disease-modifying therapies (DMTs), symptomatic treatments, EDSS score at enrollment time, burden of disease on MR imagery as well as quantitative information on the degree of physical activity at the time of enrollment.
- All information obtained during the study will be stored on a password-access database that can only be viewed and modified by the PI and co-investigators.
- All subjects enrolled in the study will be attributed a coded number and all personnel information will be de-identified upon collection. The subject codes will be maintained by study staff within the secure database only accessible by study staff and on UT Health-supported servers approved for storing PHI.

Quality control and assurance

- Staff investigators will conduct the subjective and objective assessments. All assessors will be blinded to subject group allocation and subjects will be instructed not to inform them of their allocated group.

Publication Plan

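### The only questionnaire described on activity behaviour goes to the intervention arm, once, at 6 months, so it cannot estimate the effect named in the last secondary objective

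*Combined protocol and SAP*

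**What the plan says.** The last secondary objective (Objectives) reads: "To evaluate the effect of VR exercise programs on overall behavior towards physical activity and health promotion in youth through self-report questionnaires".

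Under Study Design, in the bullet on personal sessions, "a survey questionnaire will be given to all participants enrolled in the intervention group at the 6-month follow-up time". Its subject is how far physical activity has become part of daily life. Statistics then says: "Qualitative analysis will be performed through a survey questionnaire collected at the time of the 6-month follow-up". That bullet does not repeat the restriction to one arm. Its timing and topic match, so I read the two as the same survey.

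The questionnaires that both arms complete (Study Procedures, subjective assessments) are MSIS-29, MFIS and HADS, at weeks 1 and 12 and at 6 and 12 months.

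Two other sources of activity data cover both arms:
- Study Procedures asks both groups to log sport by type and weekly duration, "to account for physical activity done outside of the active intervention". On the period: "This will be recorded during the 6-month intervention period".
- Data handling and record keeping provides for quantitative information on activity level at enrolment.

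The general analysis statement is: "Independent samples t-tests and chi-square tests will be done to assess differences between intervention and control groups on pre-trial and post-trial assessments". It names no instrument.

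**The concern.** To speak of an effect, the trial needs something to compare with: controls measured in the same way or, more weakly, the same people measured beforehand. The survey has neither. It can describe how intervention participants found the programme and how they see exercise fitting into their care, which is a sensible purpose. It cannot show that the programme changed behaviour.

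This matters because the background section treats changing exercise behaviour, and sustaining the change, as a main challenge in this age group, and this is the objective that addresses it. Followed as written, the trial could report a behavioural effect from one arm's answers at one time.

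Sending the survey to controls would not be enough on its own. Statistics states "Only participants who completed the 6-month exercise program will be included in the analysis of the intervention group", and a later bullet keeps "all of those randomized to the intervention group who completed the 12-week" programme. The two bullets give different durations, but both keep only completers in the intervention arm and set them against controls who face no such condition. Completing an exercise programme is closely bound up with exercise behaviour, so that selection would bias this comparison directly.

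**Working it through.** The documents give no power, effect size or SD, so there is no planned figure to reproduce. The main check is a side-by-side reading of every self-report source.

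| Source (section) | Arms | Times | Content | Tied to this objective? |
|---|---|---|---|---|
| Survey (Study Design; Statistics) | Intervention only | 6 months, once | Activity in daily life; experience | By topic; analysed qualitatively |
| MSIS-29 (Study Procedures) | Both | Weeks 1 and 12; 6 and 12 months | Impact of MS | No |
| MFIS (Study Procedures) | Both | As above | Impact of fatigue | No |
| HADS (Study Procedures) | Both | As above | Anxiety and depression | No |
| Sport log (Study Procedures) | Both | Months 0-6 | Type and weekly duration of sport | No |
| Enrolment activity (Data handling) | Both | Enrolment | Degree of activity, quantitative | No |

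**Survey responses available for a contrast.** Controls: 0 of 12. Baseline: 0. Intervention arm: one round. So the survey gives no between-arm difference and no change from baseline.

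**What the other sources leave open.** The log and the enrolment measure could support a between-arm comparison of reported sport to month 6, if the plan said so and the units matched. They do not reach attitudes, health promotion or months 6-12.

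**Precision if behaviour items were given to both arms.** Inputs: 12 per arm (Study Design) and alpha 0.05 (Statistics), taken as two-sided as in the primary hypothesis. All 24 are assumed to respond. The baseline correlation r is also an assumption.

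- Unadjusted 95% half-width = t(0.975, 22) × √(1/12 + 1/12) = 2.074 × 0.408 = 0.85 SD.
- Adjusted for baseline, approximately t(0.975, 21) × 0.408 × √(1 − r²), with t = 2.080:
  - r = 0.3: 0.849 × 0.954 = 0.81 SD
  - r = 0.5: 0.849 × 0.866 = 0.74 SD
  - r = 0.7: 0.849 × 0.714 = 0.61 SD
- Power of an unadjusted t-test for a true difference of 0.5 SD: 22%.
- Difference detectable at an assumed 80% power: (1.960 + 0.842) × 0.408 = 1.14 SD by normal approximation, 1.20 SD by t-test.

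The items would make the effect estimable but would not support a useful test.

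**Burden.** The three existing questionnaires have 29 + 21 + 14 = 64 items, and the protocol allows 15-20 minutes. That is 15/64 = 0.234 to 20/64 = 0.3125 minutes per item. For an assumed 10-15 items, the extra time per contact runs from 10 × 0.234 = 2.3 to 15 × 0.3125 = 4.7 minutes. Over three contacts it is 7.0 to 14.1 minutes.

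**The case against.** The strongest reply is that the plan may already hold what is needed. The list of subjective assessments may not be exhaustive, the objective speaks of questionnaires in the plural, and the Study Schedule and Data Acquisition Form are listed but not shown. An activity instrument, or the units of the enrolment measure, could be there. This stands as a limit: the finding concerns the text available.

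A second reply is that both-arm activity data exist. This also stands. A reader might infer that the trial has no control or baseline information on activity; the log and the enrolment measure show otherwise. Nor does it count against them that the general t-test statement omits them, since it names no instrument at all.

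A reader might also infer that the log, being meant for activity outside the intervention, loses the prescribed VR time (3 × 45 = 135 minutes a week). The documents do not support that. Study Procedures also provides exercise logs for the weekly sessions and requires additional VR time to be documented. Non-VR sport is, besides, a legitimate measure of whether behaviour changed beyond the assigned sessions.

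Third, a new both-arm measurement with a half-width of 0.85 SD tells little, and rewording the objective is cheaper. The imprecision is real, so the result should be exploratory. Rewording is a sound fallback, but it gives up the question.

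Finally, completer-only analysis is a trial-wide issue, and changing it for one objective would leave mixed analysis sets. That is fair. It is raised here only because a both-arm behaviour comparison would inherit the selection.

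**Conclusion.** The concern holds, as a minor one. In the text available, the survey cannot estimate the effect that the objective names: it has no control responses and no baseline responses, and its analysis is qualitative. MSIS-29, MFIS and HADS, as the protocol describes them, do not fill the gap. The sport log and enrolment activity could fill part of it, for reported sport to month 6, but the plan does not link them to this objective.

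This rests on reading the survey bullets in Study Design and Statistics as one survey, and on the unseen attachments naming no further instrument. The precision figures also assume full response at 12 v 12 and, where adjusted, an assumed baseline correlation.

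The primary cognitive comparison is not affected. The survey remains sound as a description of intervention-arm experience.

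**What to change.** 1. Give the survey's activity and health-behaviour items to both arms at week 1, 6 months and 12 months, alongside the questionnaires both arms already complete. Keep the items on the VR experience as an intervention-only qualitative survey.
2. Name the both-arm sport log as a further measure for this objective to month 6. Report non-VR activity and total activity (adding logged VR time) separately. Adjust for enrolment activity where the units allow.
3. Compare arms as randomised, and ask intervention participants who do not complete the programme to return the items too. Adjust for baseline, report estimates with 95% confidence intervals, and label them exploratory. Say explicitly that the analysis set for this objective is not restricted to completers. Attribute any difference to VR plus education, since the education sessions go only to the intervention arm.
4. If no both-arm measure is used, restate the objective as descriptive of intervention-arm experience.

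Steps 1-3 need a minor amendment and about 2-5 extra minutes per participant at each of three existing contacts (7.0 to 14.1 minutes in all, on the assumptions above), with no new visits. Finalising the items, ethics review and analysis time are not costed here. The answers remain unblinded self-report with low precision. Step 4 costs only wording.
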